## Additional measures to be collected

Current symptoms will be rated by means of the Positive and Negative Symptom Scale (PANSS; Kay et al. 1987) at Baseline, Days 28 and 56, Endpoint, and at 8 weeks post-training follow up. As per new FDA requirements governing management of suicidality in clinical trials, the Columbia-Suicide Severity Rating Scale (C-SSRS) will be administered at these same time points. Anticholinergic load of current medications will be calculated as per methods of Vinogradov et al. (2009b) and used as a covariate in the analyses because this factor can affect cognitive gains in cognitive training studies.

### Additional Fitness Measures for Specific Aim 2.

1. 400 Meter Walk. Participants will be asked to walk at their usual pace, without over-exerting. They can stop for up to 1 min for fatigue or other symptoms. A time limit of 15 minutes to perform the test has been established based on the following considerations. First, individuals who complete the walk in >15 minutes have an extremely slow pace (<0.44 m/sec), which would make their walking capacity of little utility in daily life. Second, selecting a higher cut-point, such as 30 or 60 minutes makes the objective assessment impractical and does not add to the clinical significance of the outcome. Participants will be allowed to use a cane, but not a walker, to complete the 400 m walk. Procedurally, we will first request that participants attempt the walk without the use of a cane. Those who feel unsafe will be allowed to attempt the walk with their cane.
2. Walking and Walking While Talking. Participants will be asked to walk across an electronic walk way which captures walking speed and foot placement in a quiet well-lit hallway wearing comfortable footwear. Start and stop points 10 meters apart will be marked by lines on the floor and include 3 feet from the walkway edge for initial acceleration and terminal deceleration. Seven walking trials will be randomly conducted; 3 single task walking only trials and 4 dual-task walking while talking trials. For the walking while talking trials participants will be asked to recite alternating letters of the alphabet. The order of the initial letter will randomly vary between "A" and "B" to minimize practice effects and/or count backwards by 3's (Guralnik et al. 2000).
3. Short Physical Performance Battery (SPPB). The SPPB is based on a timed short distance walk, repeated chair stands and a balance test (as described by Guralnik et al.[17]). The battery will be administered by a trained and certified examiner.

Measure	Screen/ Weeks		Weeks		Weeks		Endpoint	20 weeks
	Baseline	1-4	Day 28	5-8	Day 56	9-12	Day 84	8 wk F/U
Consent, HIPAA	X							
Psych, Medical Hx	X							
SCID	X							
Urine Toxicology	X						X	X
PANSS	X		X		X		X	X
C-SSRS, re suicide	X		X		X		X	X
Randomization	X							
AE vs. CONT: 3 sessions/wk		X		X		X		
MCCB	X						X	X
VO 2 max	X						X	X
400 Meter Walk	X						X	X
Walking+Talking	X						X	X
SPPB	X						X	X
UPSA	X						X	X
SLOF	X						X	X

See Table 3 for **Timeline**. We will track the attendance of each participant, and will call to ascertain the reasons for missed sessions. Reasons will be compiled as pilot data for planning a larger study.

**Statistical analysis plan**  
**Specific Aim 1:**  
 Compare the feasibility and effectiveness of AE

training to a CONT condition at the end of treatment (12 weeks) in VA participants with SCZ or schizoaffective disorder. We predict that the completion of this training will be feasible in our VA population, and that the AE group will exhibit significantly greater improvement on the MCCB than the CONT group.

**Statistical analysis:** Basic statistical comparisons will be performed preliminarily before using a unified statistical approach. Two-sample t-tests using the change in cognitive tests and functional scales as dependent variables will compare AE to CONT participants. The statistical methodology includes both initial descriptive comparisons followed by a more complex unified statistical approach. Spec Aim 1 will ultimately be addressed in a full Merit project using a linear mixed model that is conceptually similar to analysis of variance (ANOVA). However, in this Pilot proposal we will build intuition about the model and the expected results by performing simple comparisons of direct interest prior to complex modeling. To accomplish this preliminary descriptive step and test our hypothesis we will use a univariate analysis of covariance (ANCOVA) looking at change scores with baseline measures plus age, sex, and anticholinergic load as covariates. We predict that greater anticholinergic load of medication will predict poorer improvement. With a sample size of 20 completers per treatment group, we will be sensitive to a within-between interaction effect size of  $f=0.456$  at an alpha level of 0.05 with a power of 0.80. This can be interpreted as a sensitivity to between group difference in change scores of 9.5 MCCB composite t-score units (mean=50, SD=10), which is a meaningful clinical effect.

We will also undertake exploratory (non-inferential) analyses to estimate the strength of association of multiple dependent measures from the cognitive and functional domains. Data reduction via factor analysis will be performed for the MCCB battery data to reduce the number of dependent measures. Because the analysis of this data will employ multiple independent analyses, uncorrected significance tests will not be appropriate for inferential interpretation. However, uncorrected p-values will be reported as arbitrary criteria of effect size strength in deference to widespread use in social science for exploratory analyses.

To assess feasibility we will collect data on the numbers of SCZ participants who are potentially interested in participation, the number who screen out and for what reasons, the number of drop outs, and the reasons for their dropping out. We will also collect data on attendance and barriers to attendance. For these measures we will compute descriptive statistics. These data will inform proposals for fully powered future studies.

**Specific Aim 2:** Evaluate whether increases in cardiovascular fitness ( $VO_2\text{max}$ ) mediates cognitive improvement. We predict that the degree of estimated  $VO_2\text{max}$  improvement in the AE group will predict the degree of cognitive improvement with training.

**Statistical analysis:** We will assess potential mediator effects of  $VO_2\text{max}$  as well as potential moderator effects of age, sex, and anticholinergic load to better formulate covariates in future models. The association between potential moderators and cognitive improvement will be evaluated through use of bivariate and multiple correlations; only significant associations will be further assessed as possible moderators. The assessment of  $VO_2\text{max}$  as a potential mediator will be evaluated using partial correlation coefficients from the regression model. With a total sample size of 20 participants in the treatment group, we will be sensitive to a bivariate effect size of  $r = 0.428$  at an alpha level of 0.05 with a power of 0.80. This would allow us to detect differences of up to 18% in potential moderator variables. In a multiple regression with four predictor variables (because of issues of multicollinearity with anticipated high degrees of correlation possible between the potential moderator variables, it is doubtful that we will have a viable model with more than four predictors), we will be sensitive to an overall effect size of  $f^2 = 0.063$ . Although sensitivity is provided, we consider the analyses used in the evaluation of this pilot data to be focused on estimation of effect sizes for future studies rather than for inferential interpretation. Because of this, p-values (and criterion alpha levels) will not be corrected for multiple independent testing. We will also run an exploratory regression model with mean training hours per week.

**Specific Aim 3:** Compare changes in performance-based measurement of functional abilities (by the UPSA) in the AE vs. CONT training groups. We predict that the AE group will have greater improvement in the UPSA than the CONT group at the end of treatment and at three months follow up.

**Statistical analysis:** The statistical approach for Spec Aim 3 will be similar to that of Spec Aim 1. Descriptive statistics will be generated with 95% confidence that our sample-based estimates will be within 0.20 SD of the population values. Hypotheses will be tested (and effect size estimates will be generated) with a univariate ANCOVA looking at change scores with baseline measures plus age, sex, and anticholinergic load as covariates. With a total sample size of 20 participants per group we will be sensitive to an effect size in UPSA scores of  $f=0.481$  (alpha=0.05: power=0.80). This power and effect size will enable us to detect changes in UPSA scores of about 14%, a clinically meaningful change. A similar analysis (with identical sensitivity) will be used to assess the stability of the treatment effect through a univariate ANCOVA of change scores between the post-treatment and 3 month follow up measurements with post-treatment scores used as the covariate.

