### **Primary and secondary outcome measures**

#### **(1) Primary outcome measures:**

Measurement and Treatment Research to Improve Cognition in Schizophrenia Consensus Cognitive Battery (**MCCB**). The National Institute of Mental Health funded the development of a consensus battery of neurocognitive tests for use in SCZ cognitive trials. The result is the MATRICS Consensus Cognitive Battery (MCCB). It assesses seven key cognitive domains relevant SCZ: processing speed, attention/vigilance, working memory, verbal learning, visual learning, reasoning and problem solving, and social cognition. The MCCB has excellent test-retest reliability (Nuechterlein et al. 2008). It is the recommended outcome measure for SCZ cognition trials (Keefe et al. 2010). *The MCCB composite score at 12 weeks will be the primary outcome measure.*

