## Sample size determination

Sample size calculations for our primary outcome measure (MCCB) are based on several studies of AE compared to a control condition in which the effect sizes average approximately 0.5 (Dustman et al. 1984; Fabre et al. 2002; Heyn et al 2004; Hotting et al. 2012; Chapman et al. 2013). We also based estimated power on studies of cognitive remediation in SCZ, including a meta-analysis (Wykes et al. 2011) and studies of Posit Science computerized remediation (Fisher et al. 2010). The average effect size of the above studies is 0.5. With alpha set at 0.05, an effect size of 0.5 will yield a power of 0.80 for our **planned sample size of 20 completers per treatment group (with dropouts replaced)**. This sample size will be adequate to detect significant between group differences in MCCB change scores. More importantly for a pilot study, this sample size will allow us to estimate effect sizes specific to the target Veteran population with sufficient confidence to be useful in determining the sample size required for a future full Merit Review proposal (if indicated by the results of this pilot study). Participant retention will be an important issue. We estimate liberally from our prior work (cognitive remediation study) that *dropouts will be approximately 25%, so we will need to recruit 53 subjects in order to obtain the 40 completers needed for analysis.*

**Roles of members of the research team.** Please see delineation of roles in Budget Justification.

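### The Aim 1 effect size f=0.456 is right for the planned ANCOVA, but it converts to 9.1 MCCB units at SD 10, not 9.5; the SD is unsupported, and the sample size section's power claim disagrees with it

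*Combined protocol and SAP*

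**What the plan says.** Three statements bear on what the primary comparison can detect.

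- **Statistical analysis plan, Specific Aim 1.** The sensitivity statement opens "With a sample size of 20 completers per treatment group" and continues "we will be sensitive to a within-between interaction effect size of" f=0.456, "at an alpha level of 0.05 with a power of 0.80". It then reads this as a difference between the groups in change of "9.5 MCCB composite t-score units (mean=50, SD=10") and calls that clinically meaningful. The test of the hypothesis is a univariate ANCOVA "looking at change scores with baseline measures plus age, sex, and anticholinergic load as covariates". Two-sample t-tests of change are listed as a preliminary step.
- **Sample size determination.** For the same outcome, alpha and number of completers, it says that "an effect size of 0.5 will yield a power of 0.80". It does not say whether 0.5 is Cohen's d or Cohen's f.
- **Primary outcome measures.** The only information on the correlation between repeated scores is qualitative: "The MCCB has excellent test-retest reliability". No SD of change and no baseline-to-12-week correlation is given.

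**The concern.** The Aim 1 paragraph gives an effect size, an SD and a difference in units, and the three do not agree. The SD is that of one T-score, whereas the analysis concerns change adjusted for baseline, whose residual spread depends on a correlation that the plan does not state. The sample size section then gives 80% power at a nominal effect well below the d of 0.91 that the Aim 1 figure implies, with nothing to reconcile them.

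At stake is what the trial can claim about its own sensitivity. The 9.5 is the plan's only figure for the primary comparison in MCCB units. The sample size section also says that the pilot's more important use is to size a later full trial, so an unsupported SD and two incompatible sensitivity claims could be carried into that design.

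**Working it through.** **Inputs.** N = 40 completers, 20 per group; alpha 0.05 (taken as two-sided, since the plan does not say); power 0.80; f = 0.456; SD = 10; stated difference 9.5 units. All are from Specific Aim 1. Covariates: baseline, age, sex and anticholinergic load, so the error df are 40 - 2 - 4 = 34.

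**Step 1. Reproduce f.** Use a noncentral F with lambda = f² x N and df (1, 34). At f = 0.456, lambda = 0.2079 x 40 = 8.32 and power = 0.800. The stated f reproduces exactly. Without covariates (df 1, 38) the value would be 0.4546.

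**Step 2. Convert to units.** For two equal groups, d = 2f, and difference = 2 x f x SD.

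- d = 2 x 0.456 = 0.912
- Difference at SD 10 = 0.912 x 10 = 9.12 units
- Gap from the stated figure = 9.5 - 9.12 = 0.38 units, about 4%
- In reverse, 9.5 units at SD 10 is f = 9.5 / 20 = 0.475, where power is 0.83

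Other direct routes at SD 10 also miss 9.5: two-sided t-test 9.09, one-sided t-test 8.01, normal approximation 8.86.

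**Step 3. Which SD?** Let rho be the baseline-to-week-12 correlation, with SD 10 at both times. The SD of raw change is 10 x sqrt(2(1 - rho)). With baseline in the model, the residual SD is 10 x sqrt(1 - rho²), leaving aside anything the other covariates explain. Multiplying each by 0.912:

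| Assumed rho | SD of raw change | Detectable, raw change | Residual SD, baseline-adjusted | Detectable, ANCOVA |
|---|---|---|---|---|
| 0.5 | 10.0 | 9.1 | 8.66 | 7.9 |
| 0.7 | 7.75 | 7.1 | 7.14 | 6.5 |
| 0.8 | 6.32 | 5.8 | 6.00 | 5.5 |
| 0.9 | 4.47 | 4.1 | 4.36 | 4.0 |

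The rho values are assumptions. An SD of 10 equals the SD of raw change only at rho = 0.5. The 9.5 is matched exactly by an SD of 9.5 / 0.912 = 10.42, which as an SD of raw change needs rho of about 0.46. The baseline-adjusted residual SD cannot exceed 10 when the sample SD is 10, so the planned ANCOVA's detectable difference is then at most 9.12.

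**Step 4. Check the sample size section.** Same ANCOVA, N = 40:

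- 0.5 read as d: f = 0.25, lambda = 0.0625 x 40 = 2.5, power = 0.34
- 0.5 read as f: lambda = 0.25 x 40 = 10, power = 0.87

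Neither reading gives 0.80.

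**The case against.** The best defence is that little here does harm. The effect size is right for the planned test, the provable slip is 0.38 T-score units, and it errs on the safe side: at SD 10 a true difference of 9.5 has power 0.83, so the promised 80% is met. A completed trial is read from its estimate and confidence interval, not from a planning figure, and this pilot puts estimation first. All of that stands, and it limits the weight of the unit slip. It does not remove the conflict with the sample size section, and Specific Aim 1 does say that the ANCOVA will test the hypothesis.

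Three stronger readings are tempting, but the documents do not support them.

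- **That the interaction label shows the wrong design was powered.** On the repeated-measures scale that builds in rho, the 80% power value would be 0.23 at rho 0.5, which makes 0.456 look misplaced. But the MCCB is compared at one baseline and one 12-week visit, and with two time points the group-by-time interaction is the same test as the unadjusted comparison of change. On the lambda = f² x N scale it gives 0.4546. The plan's next sentence also reads f as a difference in change scores. The label is imprecise; the test is not wrong.
- **That SD 10 is shown to be wrong.** It is unsupported. A general statement that reliability is excellent is not a 12-week correlation in this sample, and the residual formula itself assumes that the trial sample has the normative SD of 10, which the plan does not establish.
- **That the true detectable difference is about half the stated one.** That needs rho near 0.9, which is only an assumption.

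It can also be said that the 0.5 has no stated metric. Read as f, the metric used in the Aims, it would understate power rather than overstate it. The section draws the 0.5 from averages over published studies, which makes d the likelier reading, but the point does not depend on the choice: 0.80 is wrong either way.

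**Conclusion.** The point holds in limited form. With 20 completers per group the planned ANCOVA has 80% power for an adjusted standardised difference of 0.91. At the plan's own SD of 10 that is 9.1 MCCB units, so the stated 9.5 is about 4% too large. The SD is unsupported for a baseline-adjusted change. If the sample SD is 10, the detectable difference is at most 9.1 units, and 7.9 to 4.0 over assumed rho of 0.5 to 0.9, so 9.5 is conservative for the ANCOVA. A sample SD above 10 would raise these figures in proportion.

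The more consequential item is the disagreement between sections. Power 0.80 at an effect size of 0.5 does not follow from 20 per group: it is about 0.34 if 0.5 is d, or about 0.87 if it is f. The results rest on a two-sided alpha of 0.05, 40 analysed completers and four covariates.

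**What to change.** - **Specific Aim 1.** State that 20 completers per group give the four-covariate ANCOVA 80% power for an adjusted standardised difference of 0.91 (f=0.456). Give this as about 9.1 MCCB units if the residual SD is 10, with the range over assumed correlations (7.9, 6.5, 5.5 and 4.0 units at 0.5, 0.7, 0.8 and 0.9), or replace the range with one value if a justified SD of change or residual SD is available.
- **Label.** Describe f as the between-group ANCOVA effect size. This is a clarification and does not correct the test.
- **Sample size determination.** Name the metric of the 0.5 and restate the power to agree with Aim 1: about 0.34 at d=0.5, or 0.80 at d=0.91.

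The cost is wording only. Sample size, analysis and conduct stay as they are.

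### Uncorrected p-values are set as criteria of effect-size strength in a pilot meant to estimate effects, and no confidence interval is planned for any treatment effect or association

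*Combined protocol and SAP*

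**What the plan says.** Under Specific Aim 1 of the Statistical analysis plan, beyond the main comparison, the plan describes "exploratory (non-inferential) analyses to estimate the strength of association of multiple dependent measures from the cognitive and functional domains". It warns that "uncorrected significance tests will not be appropriate for inferential interpretation", and then adds that "uncorrected p-values will be reported as arbitrary criteria of effect size strength in deference to widespread use in social science for exploratory analyses". No threshold, ranking rule or reporting filter is attached to that sentence.

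Under Specific Aim 2 the plan says that "p-values (and criterion alpha levels) will not be corrected for multiple independent testing", because the pilot is focused on estimating effect sizes for later studies. Yet it also screens age, sex and anticholinergic load by their association with cognitive improvement. Only those reaching significance are examined further as moderators, and the stated purpose is to choose covariates for future models.

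Under Specific Aim 3 effect-size estimates are promised alongside the ANCOVA, with no interval named. The only 95% statement in the plan is there, and it concerns the precision of descriptive statistics. The Sample size determination section again gives effect-size estimation for a future full study as the more important purpose of the pilot.

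**The concern.** The plan declines to use p-values for inference and then gives them a task they cannot do. A p-value combines the size of an effect with its variability and the number of people. In a trial this small, a moderate effect will often have p above 0.05 simply because the estimate is imprecise. A reader who takes p as the criterion of strength would call that effect weak.

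What the next study needs is each estimate and the range of values compatible with it, and the plan does not commit to giving that range. Where the plan does select on p, in the moderator screen, the associations that survive will on average look stronger than they are. They would then shape the covariate set of the next trial.

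**Working it through.** **Inputs from the documents.** Between-arm analyses: "With a sample size of 20 completers per treatment group", so 40 in total. The Aim 1 sensitivity is stated "at an alpha level of 0.05 with a power of 0.80", with f=0.456. The ANCOVA has four covariates (baseline, age, sex, anticholinergic load). Aim 2 associations are stated for 20 people in the treatment group. The expected effect size is 0.5 (Sample size determination).

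**Assumptions.** Tests are two-sided (not stated). The effect of 0.5 is a standardised mean difference d (metric not stated). The moderator screen has n=20, taken from the stated treatment-group size.

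**Step 1: the plan's own figure.** The sentence at issue contains no number, so the check is on the Aim 1 sensitivity beside it. Error df = 40 - 2 - 4 = 34, and the noncentrality is f² × N = 0.456² × 40 = 8.32. The noncentral F distribution gives power 0.800. The figure reproduces.

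**Step 2: what p says about a moderate difference.** With 20 per arm, t = d / √(2/20).
- d=0.5: t = 0.5 × √10 = 1.58 on 38 df, p=0.12. The 95% CI (noncentral t) is -0.13 to 1.13.
- d=0.3: p=0.35, CI -0.33 to 0.92.
- d=0.8: p=0.016, CI 0.15 to 1.44.

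The significance threshold is |d| = 2.024 × √(2/20) = 0.64, which is above the effect the plan expects.

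**Step 3: the same association at two sample sizes.** t = r√((n-2)/(1-r²)), with intervals by Fisher's z.

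| r | n | t | p | 95% CI |
|---|---|---|---|---|
| 0.40 | 20 | 1.85 | 0.081 | -0.05 to 0.72 |
| 0.40 | 40 | 2.69 | 0.011 | 0.10 to 0.63 |

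The strength is the same and the p-values differ about sevenfold (0.081 / 0.011 = 7.4).

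**Step 4: the moderator screen in Aim 2.** The critical correlation is t/√(t² + n - 2). At n=20 this is 2.101/√(2.101² + 18) = 0.444. In 100,000 simulated samples of 20 with a true r of 0.3, 26% pass, and those average |r| = 0.55, about 1.8 times the truth. If the screen were run on all 40 participants, the threshold would be 0.312.

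**Step 5: a p<0.05 filter on treatment effects, if one were applied.** The plan does not state such a filter, so these figures are conditional.
- Unadjusted comparison, 20 per arm, true d=0.5 (400,000 simulated trials): 34% pass and average 0.87, and 0.87/0.5 = 1.74, an overestimate of about 74%.
- Baseline-adjusted ANCOVA: the overestimate is about 50%, 31% and 18% for assumed baseline correlations of 0.5, 0.7 and 0.8, with about 43%, 58% and 73% passing. The documents give no baseline correlation.
- No filter: the average estimate is 0.51, so nearly unbiased.

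**The case against.** The plan is more careful than the one sentence suggests. It calls the criteria arbitrary and disclaims inference. It plans effect-size estimates under Aim 3, by an approach described as similar to Aim 1, and names estimation as the purpose elsewhere. A reader might infer that p-values are to be the measure of effect size and replace the estimates, but the text does not say so. This stands. The narrower fault remains: p is given a role as a gauge of strength, and no interval accompanies the estimates.

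A reader might also infer that the outcomes will be put in the wrong order. For between-arm outcomes with the same 20 per arm and the same model, p gives exactly the order of the absolute standardised effect. Mis-ranking arises only where n differs, through missing data or when a treatment-arm association is set beside an analysis of all 40. No section specifies a pooled correlation on 40 people. This also stands.

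A third inference is that only exaggerated effects will be kept, with the 74% figure as the consequence. The Aim 1 sentence says p-values will be reported. It does not say that results with large p will be dropped. The 74% also belongs to the unadjusted comparison, while the hypothesis test is a baseline-adjusted ANCOVA, for which the inflation is smaller. It cannot be given as the expected bias of this plan. The selection that the plan does state is the moderator screen.

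**Conclusion.** The point holds in a limited form. The Aim 1 sentence gives p-values a role that does not fit the stated purpose, and the plan names no confidence interval for any treatment effect or association. The practical consequence is that imprecise effects may be read as weak. At the plan's own expected effect of 0.5, an observed value of that size has p=0.12 and an interval from slightly below zero to above 1.

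The only documented selection on p is the Aim 2 moderator screen. With 20 people it passes only |r| above 0.44 and would show a true 0.3 as about 0.55. That rests on the screen being run in the treatment group. If significance were also used to pick treatment effects, the overestimate at a true d of 0.5 would run from about 18% to 74%, depending on adjustment and an assumed baseline correlation. The documents do not say that this will happen, and they do not support a claim that outcomes will generally be mis-ordered.

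The primary MCCB analysis is not touched. This is a cheap improvement and does not threaten the trial's main conclusion.

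**What to change.** 1. **Specific Aim 1.** Delete the wording that makes p-values criteria of effect-size strength. Replace it with, for example: *Every exploratory and secondary measure will be reported as an estimate with its 95% confidence interval, whatever its p-value. Strength will be judged from the estimate and interval. P-values may be shown but will not be used to grade or select effects.*
2. **What to report.** For between-arm measures, give the baseline-adjusted AE minus CONT difference in raw units and in standardised units. For Aim 2, give the correlation. State the n for each.
3. **Specific Aim 2.** Replace the significance screen by reporting all three named candidate moderators (age, sex, anticholinergic load) with estimates and 95% CIs, and state whether the analysis uses the treatment group or all 40 participants. This step is needed as well as the intervals, because intervals alone do not remove the bias from selecting on p.

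The cost is SAP wording. The ANCOVAs and correlations already planned produce the intervals, no extra data are needed, and the primary MCCB test and the Aim 3 hypothesis test stay as they are. The one drawback is that wide intervals become visible, which is information the next study's planners need.

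### Aim 2's overall f² = 0.063 is far below what 20 or 40 participants can detect at 80% power (that needs N = 195), and its r = 0.428 fits N = 40, not the stated 20.

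*Combined protocol and SAP*

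**What the plan says.** The figures are in the statistical analysis plan under Specific Aim 2, which treats VO₂max as a potential mediator and age, sex and anticholinergic load as potential moderators of cognitive improvement.

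- **Correlation.** "With a total sample size of 20 participants in the treatment group, we will be sensitive to a bivariate effect size of" r = 0.428, at alpha 0.05 and power 0.80.
- **Interpretation.** "This would allow us to detect differences of up to 18% in potential moderator variables".
- **Regression.** With four predictors, "we will be sensitive to an overall effect size of" f² = 0.063. This sentence gives no N, alpha or power of its own.
- **Use of significance.** For moderators, "only significant associations will be further assessed as possible moderators". The stated purpose is to help formulate covariates for future models.
- **Status.** The plan describes the analyses as "focused on estimation of effect sizes for future studies rather than for inferential interpretation".

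The whole trial has 40 participants, 20 per group (Study Design; Sample size determination).

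**The concern.** The two figures look incompatible with the sample and with each other. A correlation of 0.428 is 18% of variance from one predictor. The next figure claims that a four-predictor overall test detects about 6% of variance. Testing more predictors jointly in the same sample costs power, so the regression's detectable effect should be the larger one.

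The figures are offered as what the pilot can detect. A reader who takes f² = 0.063 at face value could read a non-significant regression as evidence against effects near 6% of variance. The design reaches 80% power only at about 45% (n = 20) or 25% (N = 40). The plan says the pilot should inform a larger trial, so an overstated sensitivity could carry into that planning.

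**Working it through.** **Inputs.** From Specific Aim 2: n = 20, alpha 0.05, power 0.80, r = 0.428, four predictors, f² = 0.063. From Study Design: N = 40 in total. Assumptions: two-sided tests, and alpha 0.05 and power 0.80 carried over to the f² sentence.

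**1. Trying to reproduce r = 0.428**

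The critical correlation is t/√(t² + n − 2), with t the 97.5% point on n − 2 df.

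- n = 20: 2.101/√(2.101² + 18) = 0.444. An observed r of 0.428 would not reach p < 0.05.
- N = 40: 2.024/√(2.024² + 38) = 0.312.

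Approximate power by Fisher z is Φ(atanh(r)·√(n − 3) − 1.96), with atanh(0.428) = 0.457.

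- n = 20: Φ(1.89 − 1.96) = 0.47.
- N = 40: Φ(2.78 − 1.96) = 0.79.

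The exact bivariate-normal calculation gives:

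| | n = 20 | N = 40 |
|---|---|---|
| Power at r = 0.428 | 0.49 | 0.80 |
| r detectable with 80% power | 0.58 | 0.43 |
| Share of variance (r²) | 34% | 18% |
| 95% CI around an observed r of 0.428 (Fisher z) | −0.02 to 0.73 | 0.13 to 0.65 |

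The smallest N giving 80% power for r = 0.428 is 40. A one-sided test does not rescue n = 20: power is 0.62 and the detectable r is 0.53. The figure therefore reproduces at N = 40 and not at the stated 20.

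**2. Trying to reproduce f² = 0.063**

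The overall F test with four predictors has 4 and N − 5 df and noncentrality λ = f²·N. At f² = 0.063, λ is 1.26 for n = 20 and 2.52 for N = 40.

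| | n = 20 | N = 40 |
|---|---|---|
| Power at f² = 0.063 | 0.10 | 0.19 |
| Overall f² detectable with 80% power | 0.816 | 0.341 |
| As R² = f²/(1 + f²) | 0.449 | 0.255 |
| Ratio to 0.063 | about 13 | about 5 |

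80% power at f² = 0.063 needs N = 195 (power is 0.799 at N = 194). Other readings do not help:

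- One coefficient out of four: N = 127.
- 0.063 read as R²: N = 183.
- λ based on the error df: N = 200.
- One predictor at alpha 0.10: N = 100.
- Overall test at alpha 0.20: power is still only 0.32 (n = 20) and 0.45 (N = 40).

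**3. A check that needs no power assumption**

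f² = 0.063 is R² = 0.063/1.063 = 0.059. The smallest observed R² giving p < 0.05 is 4F/(4F + N − 5), with F the 95% point on (4, N − 5) df.

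- n = 20: F = 3.056, so 12.22/27.22 = 0.449. That this equals the detectable R² above to three decimals is a coincidence.
- N = 40: F = 2.641, so 10.57/45.57 = 0.232.

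Four predictors of pure noise give an average R² of 4/(N − 1), which is 0.211 at n = 20 and 0.103 at N = 40. The stated effect is smaller than the R² expected from noise alone.

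**4. The two figures against each other**

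r = 0.428 gives r² = 0.183 and f² = 0.183/0.817 = 0.224 from one predictor. At the same N, alpha and power, a four-predictor overall test cannot have a smaller detectable f². Conversely, at N = 195, where 0.063 would be right, the detectable r is 0.20 and not 0.428.

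**5. The 18%**

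0.428² = 0.183. This is the smallest share of variance detectable with 80% power. It is a minimum, not an upper limit, and not a difference in a moderator.

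**6. Is a mislabelled N plausible?**

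Specific Aim 3 introduces its two-group analysis in nearly the same words: "With a total sample size of 20 participants per group we will be sensitive to an effect size in UPSA scores of" f = 0.481. Specific Aim 1 says "With a sample size of 20 completers per treatment group, we will be sensitive to a within-between interaction effect size of" f = 0.456. With two groups, four covariates (baseline, age, sex, anticholinergic load) and N = 40, the f detectable with 80% power is 0.4560, which matches. A total of 20 would give 0.674. So at least one neighbouring figure was computed on all 40.

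**The case against.** The strongest reply is that the plan itself disclaims inference for Aim 2. The sample size rests on the MCCB comparison, and no participant number, primary test or procedure depends on these figures. That stands, and it limits the consequence. It does not make the printed sensitivities correct, and nothing elsewhere in the documents corrects them.

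Second, the match of r = 0.428 to N = 40 is an inference, because the calculation is not shown. This also stands. Aim 2 predicts a relationship within the AE group, so n = 20 may be deliberate, in which case r is wrong rather than N. The analysis set should be settled first and not chosen to fit the number.

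Third, the significance screen for moderators would miss true effects even with correct figures. A true r of 0.428 fails it in about 51% of trials at n = 20 and about 20% at N = 40. Those rates come from the sample size and the screening rule, not from the misprint. What the error does is present the 20% rate as if it applied to 20 participants.

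Finally, the f² sentence restates neither alpha nor power. The comparison of R² = 0.059 with the critical values 0.449 and 0.232 needs no power assumption, and the result at alpha 0.20 shows that a looser alpha does not help.

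**Conclusion.** The concern holds. The overall f² of 0.063 is wrong on either reading of N: power is 0.10 (n = 20) or 0.19 (N = 40), against detectable values of about 0.82 and 0.34. The correlation of 0.428 is wrong for the stated 20, where power is 0.49 and the detectable r about 0.58, and right for 40. The 18% is mislabelled. The power figures assume two-sided alpha 0.05, with 80% power as the standard for both sentences. The critical-R² check and the alternative readings show that the conclusion on f² does not hang on those assumptions.

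This should be fixed, but its reach is limited to Aim 2's stated sensitivities. The sample size, the primary MCCB comparison and the fixed ANCOVA covariates are unaffected.

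**What to change.** 1. State which participants enter the moderator correlations and which enter the regression. Decide this on the scientific question before looking at the figures.
2. Restate the sensitivities to match. For the AE arm alone (n = 20): r about 0.58, overall f² about 0.82. For all 40: r about 0.43, overall f² about 0.34. If all 40 were meant, 0.428 can stay with its N corrected. The f² must change either way.
3. Give N, alpha, sidedness, power and number of predictors beside each figure.
4. Replace the 18% statement with the minimum detectable share of variance: about 34% at n = 20 or 18% at N = 40.
5. Optionally, and in keeping with the plan's emphasis on estimation, report every moderator association with its 95% confidence interval whether or not it is significant.

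The cost is SAP wording only, with no new data, visits or participants. The stated sensitivities become less favourable.
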